**ABBREVIATIONS**

ACQ	Asthma Control Questionnaire
ADA	Anti-drug antibody
AE	Adverse event
AESI	Adverse events of special interest
ALT	Alanine transaminase
ASE	All Subjects Enrolled
AT	As Treated
ATC	Anatomical Therapeutic Chemical
CEC	Clinical Endpoint Committee
CI	Confidence Interval
CS	Corticosteroid
ECG	Electrocardiogram
eCRF	Electronic Case Report Form
ED	Emergency Department
FEV 1	Forced expiratory volume in 1 second
FVC	Forced vital capacity
GSK	GlaxoSmithKline
IDMC	Independent Data Monitoring Committee
IgE	Immunoglobulin E
IM	Intramuscular
IV	Intravenous
LFT	Liver function test
LLQ	Lower Limit of Quantification
MDP1	Mepolizumab Drug Product 1
MDP2	Mepolizumab Drug Product 2
MedDRA	Medicinal dictionary for regulatory activities
mg	Milligram
mL	Millilitres
N	Number of subjects in the treatment group
n	Number of subjects with non-missing values
NAb	Neutralising antibody
NHANES	National Health and Nutrition Examination Survey
OCS	Oral corticosteroids
OLE	Open label extension (study)
PI	Principal Investigator
PT	Preferred Term
QTc(B)	QT interval corrected by Bazett's method
QTc(F)	QT interval corrected by Fridericia's method
RAP	Reporting and Analysis Plan
RUCAM	Roussel Uclaf Causality Assessment Method
SAE	Serious adverse event
SC	Subcutaneous
SD	Standard Deviation
SE	Standard Error
SDAC	Statistical Data Analysis Centre
SOC	System Organ Class

**Trademark Information**

Trademarks of the GlaxoSmithKline group of companies
NONE

Trademarks not owned by the GlaxoSmithKline group of companies
SAS
Xolair

## 1. INTRODUCTION

The purpose of the data analyses outlined in this Reporting and Analysis Plan (RAP) is to evaluate the safety, immunogenicity and effectiveness of treatment with 100mg mepolizumab administered subcutaneously (SC) every 4 weeks in subjects with severe, uncontrolled refractory asthma.

This RAP is based on Section 8 (Data Analysis and Statistical Considerations) of the MEA115666 study protocol issued 06-Mar-2013 (GlaxoSmithKline Document Number [2012N139436\\_02](#)) and is intended for use by the Statistics & Programming Department. The data analyses produced will be used in a Clinical Study Report.

### 1.1. Revision Chronology

RAP Section	Amendment Details
	Original Reporting and Analysis Plan Effective date: 20-AUG-2013
	Reporting and Analysis Plan Amendment 1 Effective date: 06-APR-2017
	
Amendments
 
 
• Inserted additional outputs to summarise the Adverse Events of Special Interests as agreed within the Program Safety Analysis Plan (PSAP)
 
• Inserted additional table of protocol deviations
 
• Clarified that the most frequent on-treatment AEs will be defined as AEs with frequency <math>\geq 3\%</math> and not <math>\geq 2\%</math>
 
• Inserted additional tables and listings of subjects with emergent hepatobiliary laboratory abnormalities and an additional listing of all clinical chemistry results for subjects who meet the liver event criteria
 
• Removed a listing of urinalysis results as no such data is collected in this study
 

## 2. STUDY OBJECTIVE(S) AND ENDPOINT(S)

### 2.1. Study Objective(s)

#### 2.1.1. Primary Objective

The primary objective of this study is to describe the long-term safety profile of mepolizumab.

### 2.1.2. Secondary Objectives

- To provide long-term treatment with mepolizumab to subjects who participated in MEA112997.
- To evaluate the effects of mepolizumab on a range of clinical markers of asthma control.

## 2.2. Study Endpoint(s)

### 2.2.1. Primary Endpoint

- Adverse Events (AEs) including both systemic (i.e. allergic/IgE-mediated and non-allergic) and local site reactions.

### 2.2.2. Secondary Endpoints

- Frequency of positive anti-mepolizumab binding antibodies and neutralising antibodies
- Annualised rate of exacerbations
- Asthma Control Questionnaire (ACQ) score
- Forced expiratory volume in 1 second (FEV1) as measured by clinic spirometry
- Number of withdrawals due to lack of efficacy
- Number of withdrawals due to adverse events
- Number of hospitalizations due to adverse events including asthma exacerbations
- Frequency of both systemic (i.e., allergic/IgE-mediated and non-allergic) and local site reactions
- 12-Lead Electrocardiogram (ECG) to derive the following endpoints:
  - Mean change from baseline in the QTc(F) (QT interval corrected by Fridericia's method)
  - Mean change from baseline in QTc(B) (QT interval corrected by Bazett's method)
  - Maximum change from baseline for QTc(F) and QTc(B).
- Vital signs
- Clinical Laboratory Parameters

## 2.3. Statistical Hypotheses

Because the study has a single treatment arm, statistical analyses of treatment effect will not be performed. Therefore no hypotheses have been defined for this study.

## 3. STUDY DESIGN

This is a multi-centre, open-label, long term, safety study of 100mg mepolizumab administered subcutaneously in addition to standard of care in subjects with severe, refractory asthma and a history of eosinophilic inflammation. Subjects who participated in the MEA112997 trial will be offered the opportunity to consent for this study. All subjects will have experienced a gap of at least 10 months since receiving their last double-blind study medication in MEA112997.

At Visit 1 subjects will undergo an initial screening to assess their eligibility to participate in this study. This screening will include: informed consent, vital signs, update of medical history, immunogenicity status based on MEA112997 data, smoking status, prior monoclonal antibody use, and exacerbations post completion of MEA112997. Subjects meeting the Visit 1 eligibility criteria will enter the run-in period. The purpose of the run-in period is to allow for receipt and review of lab results and the ECG over-read. Visit 2 will mark the end of the run-in period.

Those subjects meeting all the inclusion criteria and none of the exclusion criteria will receive their first mepolizumab dose at Visit 2. Subjects will continue to receive mepolizumab SC injections approximately every 4 weeks until either:

- The risk/benefit profile for the subject is no longer positive in the opinion of the investigator **or**
- the subject's physician withdraws the subject **or**
- the subject withdraws consent **or**
- the sponsor discontinues development of mepolizumab **or**
- the sponsor discontinues the study in the relevant participating country **or**
- mepolizumab becomes commercially available in the relevant participating country

During the trial the vial strength used when dosing will be changed for most subjects, however this will depend on the timing of regulatory approval. The 100mg dose of mepolizumab will be reconstituted from a vial of 250mg/vial strength up until such time that the 100mg/vial strength is available at the site. Once the 100mg/vial strength is available at the site, all subjects will be dosed with 100mg mepolizumab reconstituted from the 100mg/vial strength at their next treatment visit and for the remainder of the study. This change of vial strength will be when subjects are transitioned onto the new drug product. Hereafter, the 250mg/vial strength will be referred to as mepolizumab drug product 1 (MDP1) and the 100mg/vial strength (to which subjects will transition) will be referred to as mepolizumab drug product 2 (MDP2). In the case that MDP2 is not approved for use by ethics/regulatory at a local site/country subjects will continue to be dosed with MDP1.

Subjects will remain on standard of care asthma therapy, which may be adjusted during the study, at the discretion of their physician. The use of Xolair (omalizumab) or any other monoclonal antibody will not be permitted during the course of the study.

Subjects will be monitored in the clinic approximately every 4 weeks to assess adverse events and asthma status. The Asthma Control Questionnaire-5 (ACQ) will be used to assist the investigator in assessing the subject's asthma status along with spirometry at regular intervals. Exacerbations will also be reviewed at each clinic visit. As some subjects may have previously received placebo while participating in the MEA112997 trial and are naive to mepolizumab, safety lab monitoring will be more frequent at the start of the study. Appropriate safety labs will be drawn prior to starting treatment and then at week 4, 8, 12, 24, 36 and 48. Thereafter, these will be collected every 24 weeks. Labs will also be obtained at 12 weeks after discontinuing mepolizumab. Subjects

discontinuing mepolizumab treatment should be monitored for exacerbation of their asthma.

Serum samples for anti-mepolizumab antibody measurements will be obtained from all subjects at Weeks 0, 4, 24 and 48 of the initial year, week 24 and 48 for every additional year, as well as at the Follow-up Visit. Any anti-mepolizumab antibody positive sample will be tested for neutralising antibody.

A maximum of two additional anti-mepolizumab antibody samples will be obtained; one immediately prior to the first dose and the other prior to the second dose with MDP2. If the first or second dose coincides with a visit where an immunogenicity sample is already required, it is not necessary to obtain an additional sample.

## **4. PLANNED ANALYSES**

### **4.1. Interim Analyses**

At a date agreed by the study team a data look will be performed on a subset of the data. The aim of the data look is solely to ensure that all of the required tables, figures and listings are being produced and formatted correctly, such that the output produced at the planned analysis date is correct and complete.

Interim analyses will be performed as needed in order to provide open-label safety data to inform the risk-benefit assessment of mepolizumab in severe asthma. Specifically, an interim analysis will be performed to support the initial regulatory filing of mepolizumab. A second interim will also be performed to support any possible safety updates following these submissions.

At each interim a 'cut' will be made in the data, where any data collected beyond a pre-specified cut-off date will not be included within the datasets to be reported. See Section 10, Section 11, Section 12, Section 13 and Section 14 for details of all planned analyses at these interims.

This analysis will be performed by the study statistics and programming team and not by the SDAC described below who solely support the phase III programme IDMC. The safety results from this interim analysis will be reviewed by the internal GSK mepolizumab safety review team.

Access to the results from this interim analysis will not be confidential. Specifically the results may be provided to the study team, GSK governance boards, external investigators and to regulatory authorities.

#### **4.1.1. Independent Data Monitoring Committee**

An Independent Data Monitoring Committee (IDMC) will be utilised in this study to ensure external objective review of safety issues in order to protect the ethical and safety interests of subjects and to protect the scientific validity of the study. The IDMC will review cardiovascular adverse events and all cause mortality from the following studies

in the Mepolizumab Severe Asthma Phase III Program: MEA115575; MEA115588; MEA115666 (this study); MEA115661.

The unblinded statistical analyses will be performed by an independent Statistical Data Analysis Centre (SDAC) at Duke University, North Carolina. Unblinded results will not be made available to the study team: The SDAC will communicate directly with the IDMC, and IDMC recommendations will be made to a primary contact who is external to the mepolizumab study team(s) at GSK. See IDMC Charter (available on request).

Stopping guidelines will be based on comparing event rates between mepolizumab and placebo in the two double-blind trials MEA115588 and MEA115575. The two open label studies do not include any comparator data and therefore are not part of the formal stopping guidelines.

Two event rates will be considered:

- a) SAEs (including deaths) adjudicated to be cardiovascular events in nature;
- b) all cause mortality.

Analysis will be performed based on a meta-analysis of the two studies. For the purposes of the analysis, the two mepolizumab treatment arms (75mg IV and 100mg SC) in study MEA115588 will be combined to produce an overall event rate for mepolizumab in that study. Event rates will be compared between mepolizumab and placebo using the Peto odds ratio test. An estimate and 99% CI will be produced for the odds ratio for experiencing an event on mepolizumab compared to placebo.

Non-binding statistical stopping guidelines of  $p < 0.01$  two-sided will be used for a) the analysis of SAEs deemed cardiovascular in nature and b) analysis of all cause mortality. Occurrence of either of these flags would signal further examination of available data by the IDMC, with consideration of altering the conduct of either of the studies or terminating either of the studies.

This statistical analysis will be conducted once 8 subjects in the two double blind studies have experienced SAEs adjudicated to be cardiovascular in nature. The timings of further statistical analyses after the first analysis will be determined by the IDMC.

There are no circumstances under which IDMC review of the data would lead to a recommendation to stop for efficacy of mepolizumab. Therefore no adjustment to the final alpha level for efficacy will be made based on the safety stopping guidelines.

For full details of the analyses to be provided to the IDMC by the SDAC see the IDMC statistical analysis plan (available on request).

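### Can the IDMC's first cardiovascular look, at 8 events with two-sided p<0.01, flag harm at all?

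*SAP*

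**What the plan says.** SAP 4.1.1 bases the stopping guidelines on "comparing event rates between mepolizumab and placebo in the two double-blind trials MEA115588 and MEA115575". Three sentences fix the method. First, "Analysis will be performed based on a meta-analysis of the two studies". Second, "the two mepolizumab treatment arms (75mg IV and 100mg SC) in study MEA115588 will be combined to produce an overall event rate". Third, "Event rates will be compared between mepolizumab and placebo using the Peto odds ratio test", with a 99% confidence interval for the odds ratio.

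The guideline level is p<0.01: "two-sided will be used for a) the analysis of SAEs deemed cardiovascular in nature and b) analysis of all cause mortality". It is described as non-binding. A flag on either endpoint prompts the IDMC to look further and to consider altering or ending one of those trials.

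The first analysis is triggered by event count: "This statistical analysis will be conducted once 8 subjects in the two double blind studies have experienced SAEs adjudicated to be cardiovascular in nature". The IDMC chooses when later analyses take place.

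The same section has the IDMC review cardiovascular events and deaths from four studies, including this one. It leaves the two open-label studies outside the formal guideline because they have no comparator. Full detail is left to the IDMC charter and the IDMC's own analysis plan; Protocol 9.8 likewise refers to the charter. No allocation ratio, trial size, power or detectable odds ratio for the two blinded trials appears in either document.

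**The concern.** Eight events is a small number for a 1% two-sided test. MEA115588 also compares two pooled active arms with one placebo arm. With equal arms, two thirds of its events would fall on mepolizumab with no drug effect at all, so an excess on mepolizumab is harder to show there.

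Every subject in MEA115666 receives mepolizumab and the study has no control. The blinded comparison is therefore the only formal statistical trigger for cardiovascular or mortality harm described in this SAP. If the first look can hardly fire, the absence of a flag could be taken as reassurance that it does not give. The two-sided rule also fires more readily for an excess on placebo, which is not the direction that safety monitoring is chiefly for.

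**Working it through.** The SAP states no power or triggering split, so there is no figure of its own to reproduce. Its 99% interval does agree with a two-sided 0.01 test (critical Z = 2.576).

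**Inputs.** From SAP 4.1.1: 8 events, Peto test summed over two trials, two-sided 0.01. Assumed, because not in the documents: mepolizumab share 2/3 in MEA115588 (1:1:1) and 1/2 in MEA115575 (1:1). Large-sample variance is used.

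**Formula.** Let k of the 8 events come from MEA115588. Then:

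- E = 2k/3 + (8−k)/2 = 4 + k/6
- V = 2k/9 + (8−k)/4 = 2 − k/36
- Z = (O−E)/√V

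**All 8 events on mepolizumab** (O−E = 4 − k/6):

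| k | O−E | V | Z | p |
|---|---|---|---|---|
| 0 | 4.000 | 2.000 | 2.83 | 0.0047 |
| 1 | 3.833 | 1.972 | 2.73 | 0.0063 |
| 2 | 3.667 | 1.944 | 2.63 | 0.0086 |
| 3 | 3.500 | 1.917 | 2.53 | 0.0115 |
| 4 | 3.333 | 1.889 | 2.43 | 0.0153 |
| 6 | 3.000 | 1.833 | 2.22 | 0.0267 |
| 8 | 2.667 | 1.778 | 2.00 | 0.0455 |

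The flag fires for k ≤ 2 only.

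**Seven of 8 on mepolizumab** (O−E = 3 − k/6). The most favourable case is k=0: Z = 3/√2 = 2.12, p = 0.034. At k=8, Z = 1.667/1.333 = 1.25, p = 0.211. None fires.

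**Sensitivity to the assumptions.**

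- A share of 0.60 in the three-arm trial, with 1:1 in the other, moves the 8–0 cut-off to k ≤ 3; a share of 0.75 moves it to k ≤ 1.
- A half share in both trials lets 8–0 fire at every k. Two thirds in both means it never fires.
- No 7–1 split fired at any allocation tried (mepolizumab share from one half upward).
- With finite trial sizes, k=3 just crosses 0.01 only if the 1:1 trial is small, roughly 40 to 100 subjects depending on the size of the other.
- A doubled exact p fires only at k=0 (0.0078). A continuity-corrected test never fires (0.0133 at k=0).

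The need for 8–0 is therefore robust. The cut-off in k is not.

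**Chance of a harm flag at the first look** (1:1:1 and 1:1), by share of subjects in the three-arm trial:

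| True odds ratio | 0% | 25% | 50% |
|---|---|---|---|
| 2 | 3.9% | 3.2% | 0.6% |
| 3 | 10.0% | 7.3% | 1.3% |
| 5 | 23.3% | 15.2% | 2.4% |

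The first column is (R/(R+1))^8; for R=3, 0.75^8 = 0.100.

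**Placebo direction.** Eight of 8 on placebo fires at every k, and 7 of 8 fires for k ≥ 4. With no true effect and half the subjects in each trial, the rule fires for harm 0.09% of the time and for a placebo excess 0.55%.

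**What the alternatives would do.**

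- *First test at 14 events.* If all come from a 2:1 trial, 14–0 gives Z = 4.667/√3.111 = 2.65, p = 0.0082, but 13–1 gives p = 0.038. Every event must still be on mepolizumab, and the flag chance at an odds ratio of 3 is (6/7)^14 = 12%. The 8–0 flag that works for k ≤ 2 is lost meanwhile.
- *One-sided 0.025 at 8 events.* At 1:1, both 8–0 and 7–1 fire. The false-flag rate rises from 1/256 = 0.4% to 9/256 = 3.5%, and sensitivity at an odds ratio of 3 from 10.0% to 0.75^8 + 8 × 0.75^7 × 0.25 = 36.7%. With all events at 2:1, the false-flag rate goes from 0 to (2/3)^8 = 3.9% and sensitivity from 0 to (6/7)^8 = 29%. Both false-flag rates exceed the nominal 2.5%, before repeat looks and a second endpoint.

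**The case for a change.** The strongest case for a change is that event number, test, pooling and level combine into a rule that barely responds to harm at its own trigger point, and that nothing in SAP 4.1.1 tells the reader so. A true odds ratio of 3 is missed at least nine times in ten or so. Sensitivity is greater in the less useful direction. A false flag costs only a further review, so a looser harm boundary looks cheap, and the edit is a matter of wording.

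The weakness of this one look stands, and so does the asymmetry. Four things limit what follows.

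- It is a property of the first cardiovascular look, not of the whole guideline. The IDMC may test again whenever it chooses, and deaths carry their own flag.
- The rule is non-binding. The IDMC reviews individual cardiovascular events and deaths in all four studies whatever the p-value, and under SAP 4.1 this study's interim safety results also go to the sponsor's internal safety review team.
- The SAP rules out stopping for efficacy, but it attaches the further review to a flag without naming a direction. It is not correct that a placebo excess has no consequence.
- The gain in sensitivity from a looser boundary is real, but about a ninefold rise in false flags per look at 1:1 is not negligible when the looks can be repeated on two endpoints. That choice belongs to the IDMC and the sponsor across the programme.

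**Conclusion.** No change to this plan. The arithmetic holds within its limits: at 8 events a harm flag needs all 8 on mepolizumab, provided at least half of each trial is on mepolizumab. With 1:1:1 and 1:1 allocation it also needs at most 2 of those events to come from MEA115588. The flag chance at an odds ratio of 3 is then 1.3% with half the subjects in the three-arm trial, and 10.0% if all events come from the 1:1 trial. The cut-off of 2 and these percentages rest on ratios that the documents do not give.

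Nothing in the SAP is contradicted, because it claims no operating characteristic for this look. A strict level at an early, non-binding look is a fair trade-off between missed signals and false flags, and both alternatives have costs of their own. The smallest triggering split is detail that fits the IDMC analysis plan, which was not available here. MEA115666 contributes no data to the test, so editing its SAP would not alter how the two blinded trials are monitored or how this study is analysed. The reader should simply not take an unflagged first look as evidence that there is no cardiovascular harm.

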## 5. SAMPLE SIZE CONSIDERATIONS

### 5.1. Sample Size Assumptions

There is no sample size calculation for this study. The sample size will be determined by the number of available subjects who were randomised into the MEA112997 trial and are eligible for the current study based on inclusion and exclusion criteria.

## 6. ANALYSIS POPULATIONS

The following analysis populations will be derived as required:

### All Subjects Enrolled Population

The All Subjects Enrolled (ASE) population will comprise all subjects for whom a record exists on the study database. This population will be used for summarising pre-treatment SAEs, listing AEs and summarising reasons for screen and run-in failures.

[figure not shown]
### As Treated Population

The As Treated (AT) population will consist of all subjects who received at least one dose of open label mepolizumab. This population will be the primary population for all summaries of efficacy and safety measures.

[figure not shown]
## 7. TREATMENT COMPARISONS

Due to this study having a single treatment arm, statistical analyses of treatment effect will not be performed. However, there are two comparisons which are of interest:

- 1) Reintroduction of mepolizumab vs. first time exposure: Adverse events and immunogenicity data collected during the first 6 months of treatment within MEA115666 will be summarised by treatment assigned within MEA112997. This is to assess whether subjects present differing responses to treatment dependant on whether they are being reintroduced to mepolizumab or this is their first time exposed to the drug (See [Figure 1](#) and [Table 1](#)).

**Figure 1 Presentation of Data According to Subject's Former Treatment**

- 2) Change in drug product: Adverse events, immunogenicity and blood eosinophil data will be compared before and after the change in drug product of mepolizumab to investigate whether there is a difference on the safety or efficacy profile following the transition to the new drug product (See [Figure 2](#)).

**Figure 2 Presentation of Data by Drug Product**

### 7.1. Data Display Treatment and Other Sub-group Descriptors

In the data displays the treatment groups will be identified as described in [Table 1](#). All subjects will be presented within the single treatment group of 'Mepolizumab 100mg SC'.

